# 7.7. POOLING

Data pooling will be performed as necessary for exploratory analyses, as described in Section 9.6.2. No other data pooling is planned.

## 8. DEMOGRAPHIC, OTHER BASELINE CHARACTERISTICS

#### 8.1. SUBJECT DISPOSITION AND WITHDRAWALS

The number and percentage of subjects screened, randomized, completed and discontinued, entered each study period, and in each analysis population will be summarized by age group (4-17 years, 18-55 years, 4-55 years) and treatment group (Placebo, AR101, and Total).

Reasons for discontinuation from the study will be summarized as well. In addition, subjects who discontinued study drug will be reviewed to determine if discontinuation was treatment-related and whether discontinuation was due to chronic/recurrent GI AEs. Classification of subjects will be determined during blinded data review prior to study unblinding.

Subject completion status, date of study completion/discontinuation, study treatment discontinuation, and reason for discontinuation will be listed based on the information collected in the case report form (CRF). Other information collected at screening and information regarding emergency unblinding will be included in the data listings as well.

Inclusion and exclusion eligibility will be listed separately.

#### 8.2. **PROTOCOL DEVIATIONS**

All protocol deviations as defined in Section 5 will be listed by subject. Major protocol deviations (identified by blind data review before database lock) will be summarized by age group (4-17 years and 18-55 years) and treatment group (Placebo, AR101, and Total).

#### 8.3. DEMOGRAPHIC AND OTHER BASELINE CHARACTERISTICS

Summary statistics for demographic and baseline characteristics will be provided for the Safety, ITT, Completer, and PP populations for subjects ages 4-17 and for the Safety, ITT, and Completer populations for subjects ages 4-11 years, 12-17 years, 18-55 years, and 4-55 years by treatment group (Placebo, AR101, and Total). A separate summary of demographics and baseline characteristics will be presented for screen failure subjects. Demographic data will include age, race, ethnicity, sex, body weight, height and BMI. Baseline characteristics include total IgE, ps-IgE, ps-IgG4, ps-IgE/IgG4 ratio, SPT mean wheal diameter at the 15 minute time point, MTD of peanut protein at Screening DBPCFC, and Childbearing Potential. History of asthma will also be included.

Age will be calculated relative to date of informed consent, as follows:

• If the month and day portion of the informed consent date is prior to the month and day portion of the birthdate, age will be calculated as the year of informed consent minus the year of birth, minus one;

• If the month and day portion of the informed consent date is on or after the month and day portion of the birthdate, age will be calculated as the year of informed consent minus the year of birth.

Demographic and baseline characteristic information will be listed for all randomized subjects.

# 8.4. ALLERGY HISTORY

Allergy history will be listed by subject.

The duration of peanut allergy (months since peanut allergy diagnosis), number of anaphylactic reactions to peanut in lifetime, number of anaphylactic reactions to peanut per year during lifetime, months since most recent anaphylactic reaction to peanut, months since most recent reaction to peanut that was treated with a therapy, the type of therapy administered for the most recent anaphylactic reaction to peanut, and the symptoms experienced during the most recent peanut exposure will be summarized by age group (4-17 years, 18-55 years, and 4-55 years) and treatment group (Placebo, AR101, and Total).

The reported date of the most recent reaction to peanut and date of diagnosis of peanut allergy will be imputed based on the logic in section 7.6.

# 8.5. NON-PEANUT ALLERGY HISTORY

All non-peanut allergy history will be listed by subject. The presence of non-peanut allergy history and causative allergens will also be summarized by age group (4-17 years, 18-55 years, and 4-55 years) and treatment group (Placebo, AR101, and Total).

# 8.6. OTHER MEDICAL HISTORY

Medical history will be listed by subject and body system. Subjects experience abnormal medical history events will be summarized by age group (4-17 years, 18-55 years, and 4-55 years), treatment group (Placebo, AR101, and Total) and by MedDRA system organ class and preferred term.

## 9. EFFICACY

# 9.1. PRIMARY ENDPOINT

The primary endpoint for North America is a desensitization response as determined by tolerating a single highest dose of at least 600 mg of peanut protein at the Exit DBPCFC with no more than mild symptoms. The primary endpoint for Europe is a desensitization response as determined by tolerating a single highest dose of at least 1000 mg of peanut protein at the Exit DBPCFC with no more than mild symptoms. Subjects who do not have an Exit DBPCFC are non-responders.

The number and percent of subjects with a desensitization response will be reported by treatment group. The desensitization response rate and its 95% confidence interval will be calculated for each treatment group with Wilson (score) confidence limits for the binomial proportion. The 95% confidence interval for the treatment difference (AR101 desensitization rate minus placebo desensitization rate) will be based on Farrington-Manning CI for the difference in binomial proportions. The number and percent of subjects at each dose level for highest tolerated dose at the Exit DBPCFC will also be summarized by treatment group.

The primary efficacy analysis of the primary endpoint will be evaluated in subjects ages 4-17 and will test for the difference in response rates (AR101 minus Placebo) in the ITT Population. For North America, the Farrington-Manning test will be used to test the null hypothesis that the difference is equal to 0.15 at the 0.05 significance level. AR101 is considered to have met primary efficacy endpoint if the lower bound of the corresponding test-based 95% confidence interval is greater than the pre-specified margin of 0.15.

This corresponds to the following hypotheses:

- H0: Proportion of active subjects with a desensitization response proportion of placebo subjects with a desensitization response = 0.15
- $H_A$ : Proportion of active subjects with a desensitization response proportion of placebo subjects with a desensitization response > 0.15 or < 0.15

For Europe, the Farrington-Manning test will be used to test the null hypothesis that the difference is equal to 0 at the 0.05 significance level. AR101 is considered to have met primary efficacy endpoint if the lower bound of the corresponding test-based 95% confidence interval is greater than 0.

#### 9.2. ADDITIONAL ANALYSES OF THE PRIMARY EFFICACY ENDPOINT

As a sensitivity analysis in order to determine the impact of missing data on the robustness of the study results, the primary efficacy endpoint will be analyzed using a worst case approach to missing data imputation. Placebo subjects who have missing data (i.e., do not have an Exit DBPCFC) for the primary efficacy endpoint for any reason will be considered as responders while AR101 subjects will be considered as non-responders if they have missing data for the endpoint. Analytical methods will follow those described above in Section 9.1.

If the primary analysis of the primary endpoint shows a statistically significant treatment effect, a tipping point analysis will be conducted to identify the point at which the number placebo subjects with missing data are imputed as responders will make the treatment effect non-significant. The first step will be to test the treatment effect when all AR101 subjects with missing data are imputed as non-responders and only one placebo subject with missing data is imputed as a responder while the remaining placebo subjects with missing data are imputed as non-responders. If that test shows a statistically significant treatment effect the number of placebo subjects who have missing data that are imputed as responders will be increased by one until the treatment effect becomes non-significant.

The primary efficacy analysis will be repeated in the Completer population as a sensitivity analysis and also in the PP population (if sufficiently different from the Completer population; section 4.7). Additionally, subjects with an indeterminate Exit DBPCFC as defined in section 7.5 will be excluded for a sensitivity analysis of the primary efficacy analysis in the ITT population.

The primary efficacy endpoint will be analyzed in the following subgroups in the ITT and Completer populations as supportive analyses to the primary efficacy analysis using the methods described in Section 9.3.1:

- By Region (NA and EU) in pediatric subjects
- By Pediatric Age group (Children 4-11 and Adolescents 12-17)
- By Region and Pediatric Age group (NA Children, NA Adolescents, EU Children, and EU Adolescents)

If each region stratum has at least 3 placebo subjects, then a sensitivity analysis will be conducted on the common risk difference of the response rates (AR101 minus Placebo) in the ITT Population, stratified by Region. The risk difference will be estimated using the Mantel-Haenszel estimate of the common risk difference. A 95% confidence interval will be calculated using stratified Newcombe confidence limits. The common risk difference assumption will be assessed by visual comparison of the 95% Farrington-Manning CIs across the 2 strata and by a 1 degree of freedom Wald statistic calculated to test for unequal risk differences across the 2 strata.

Similarly, if each pediatric age group stratum has at least 3 placebo subjects, then a sensitivity analysis will be conducted on the common risk difference of the response rates (AR101 minus Placebo) in the ITT Population, stratified by Pediatric Age group.

An additional similar sensitivity analysis will be conducted on the common risk difference of the response rates (AR101 minus Placebo) in the ITT Population, stratified by pediatric age group and region, if each region and pediatric age group combination has at least 3 placebo subjects.

## 9.3. KEY SECONDARY EFFICACY ENDPOINTS

If the primary efficacy analysis is significant at the 0.05 level, then analysis of the treatment effect for key secondary efficacy endpoints will be tested in the following hierarchical order:

North America:

- 1. Response at a single dose of 300 mg (443 mg cumulative) of peanut protein: The proportion of subjects ages 4-17 who tolerate a single dose of 300 mg of peanut protein with no more than mild symptoms at the Exit DBPCFC
- 2. Response at a single dose of 1000 mg (2043 mg cumulative) of peanut protein: The proportion of subjects ages 4-17 who tolerate a single dose of 1000 mg of peanut protein with no more than mild symptoms at the Exit DBPCFC
- 3. The maximum severity of symptoms in subjects ages 4-17 occurring at any challenge dose of peanut protein during the Exit DBPCFC
- 4. Response at a single dose of 600 mg (1043 mg cumulative) of peanut protein: The proportion of subjects ages 18-55 who tolerate a single dose of 300 mg of peanut protein with no more than mild symptoms at the Exit DBPCFC

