# **1.1. DOCUMENT HISTORY**

SAP Final Version 1 was approved prior to the first ARC003 subject unblinding (Dec2016). Updates for Version 2 of the SAP are being made post-unblinding of several subjects. It is important to note that all Aimmune and Agility Clinical, Inc. (Agility) staff involved in SAP development and study conduct responsibilities remain blinded to subjects' treatment assignments. The staff will remain blinded until the full study is unblinded post database lock.

Version 2 of the SAP incorporates feedback received by Aimmune from regulatory authorities on the ARC003 study protocol. The FDA correspondence was dated 13Jan2017 and notes the FDA's concern about the number of adult subjects in the study. Per the FDA, licensure of AR101 will likely be possible only in pediatric subjects ages 4-17 years. As such, the efficacy and safety endpoints have been modified in this version of the SAP and in the study protocol to note the primary population for analysis of all endpoints is in the pediatric population. The definition of EU primary and secondary endpoints were integrated in this SAP.

Other notable changes from Version 1 to Version 2 of the SAP include:

- The proportion of subjects aged 18 to 55 years who tolerate a single highest dose of at least 600 mg (for North America) and of at least 1000 mg (for EU) of peanut protein with no more than mild symptoms at the Exit DBPCFC was added as a key secondary efficacy endpoint.
- A tipping point sensitivity analysis of the primary efficiacy endpoint was added based on FDA feedback.
- The mITT population was removed as an analysis population since it was decided that sufficient sensistivity analyses of efficacy endpoints are defined in the SAP without including an mITT population.
- An SMQ search analysis of hypersensitivity events occurring with 2 hours of each other will be presented.
- Adverse event summaries combining adverse events collected on the adverse event page with including in-clinic dosing symptoms will be presented

Other changes have been made but do not materially alter analytical methods or planned summaries detailed in Final Version 1 of the SAP (dated 07Dec2016).

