#### **3.2. SECONDARY ENDPOINTS**

#### 3.2.1. Key Secondary Efficacy Endpoints

North America: The hierarchal order of key secondary efficacy endpoints is as follows:

- 1. The proportion of subjects ages 4-17 who tolerate a single highest dose of at least 300 mg (443 mg cumulative) of peanut protein with no more than mild symptoms at the Exit DBPCFC
- 2. The proportion of subjects ages 4-17 who tolerate a single highest dose of at least 1000 mg (2043 mg cumulative) of peanut protein with no more than mild symptoms at the Exit DBPCFC
- 3. The maximum severity of symptoms in subjects ages 4-17 occurring at any challenge dose of peanut protein during the Exit DBPCFC
- 4. The proportion of subjects aged 18 to 55 years who tolerate a single highest dose of at least 600 mg (1043 mg cumulative) of peanut protein with no more than mild symptoms at the Exit DBPCFC

Europe: The hierarchal order of key secondary efficacy endpoints is as follows:

- 1. The proportion of subjects ages 4-17 who tolerate a single highest dose of at least 600 mg (1043 mg cumulative) of peanut protein with no more than mild symptoms at the Exit DBPCFC
- 2. The proportion of subjects ages 4-17 who tolerate a single highest dose of at least 300 mg (443 mg cumulative) of peanut protein with no more than mild symptoms at the Exit DBPCFC
- 3. The maximum severity of symptoms in subjects ages 4-17 occurring at any challenge dose of peanut protein during the Exit DBPCFC

4. The proportion of subjects aged 18 to 55 years who tolerate a single highest dose of at least 1000 mg (2043 mg cumulative) of peanut protein with no more than mild symptoms at the Exit DBPCFC

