# **3.4. EXPLORATORY ENDPOINTS**

- The primary endpoints identified above will be repeated in the following 3 age groups: 4 to 11 years, 12 to 17 years, and 4 to 55 years, inclusive
- The first 3 key secondary endpoints will be repeated in the following 4 age groups: 4 to 11 years, 12 to 17 years, 18 to 55 years, and 4 to 55 years, inclusive
- Treatment satisfaction assessment using the Treatment Satisfaction Questionnaire for Medication (TSQM-9) and an exit survey with palatability questions

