# 6.3. MULTIPLE COMPARISONS AND MULTIPLICITY

The key secondary endpoints and other secondary efficacy endpoints will be tested in a hierarchical method, as described in Sections 9.3 and 9.5.

No other adjustments will be made for multiple comparisons.

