### 7.4. CLASSIFICATION OF RESPONDER STATUS

#### 7.4.1. Classification as a responder

To be a 600 mg responder, a subject must meet both of the following conditions:

- 1) Must have attained a maximum tolerated single dose (MTD) ≥600 mg of peanut protein on Exit DBPCFC
- 2) Must not have experienced more than mild symptoms through 600 mg of peanut protein on Exit DBPCFC.

Classification as a 300 mg responder and a 1000 mg responder are defined similarly.

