#### Europe:

- 1. Response at a single dose of 600 mg (1043 mg cumulative) of peanut protein: The proportion of subjects ages 4-17 who tolerate a single dose of 600 mg of peanut protein with no more than mild symptoms at the Exit DBPCFC
- 2. Response at a single dose of 300 mg (443 mg cumulative) of peanut protein: The proportion of subjects ages 4-17 who tolerate a single dose of 300 mg of peanut protein with no more than mild symptoms at the Exit DBPCFC
- 3. The maximum severity of symptoms in subjects ages 4-17 occurring at any challenge dose of peanut protein during the Exit DBPCFC
- 4. Response at a single dose of 1000 mg (2043 mg cumulative) of peanut protein: The proportion of subjects ages 18-55 who tolerate a single dose of 1000 mg of peanut protein with no more than mild symptoms at the Exit DBPCFC

Each comparison will be evaluated for statistical significance (two-sided p<0.05) only if all of the preceding tests in the hierarchy and the primary analysis of the primary endpoint are statistically significant in favor of AR101. Similar to the primary efficacy analysis of the primary endpoint, the ITT Population will be used as the primary population in pediatric subjects for analysis of key secondary endpoints as part of the hierarchical testing procedure. This closed testing procedure maintains the overall Type I error rate at 0.05 (EMEA CPMP, 2002; Cook et al., 2008). If any of the preceding tests are not significant, the p-value will be displayed for informational purposes only.

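### SAP 9.3 gives two different response thresholds, 600 mg and 300 mg, for the North America adult key secondary endpoint

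*SAP*

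**What the plan says.** SAP 9.3 lists the key secondary endpoints in the order in which they will be tested once the primary analysis is significant. Item 4 for North America is the adult endpoint. Its heading is "Response at a single dose of 600 mg (1043 mg cumulative) of peanut protein". The definition on the same line is "The proportion of subjects ages 18-55 who tolerate a single dose of 300 mg of peanut protein".

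SAP 3.2.1 states the same endpoint, also as item 4 of the North America order, as "The proportion of subjects aged 18 to 55 years who tolerate a single highest dose of at least 600 mg". The list of Version 2 changes in SAP 1.1 also gives 600 mg for North America, as do the protocol synopsis, protocol 3.7.1 and protocol 9.2.2.1.

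On multiplicity, SAP 6.3 says: "The key secondary endpoints and other secondary efficacy endpoints will be tested in a hierarchical method, as described in Sections 9.3 and 9.5". SAP 7.4.1 defines a 600 mg responder and then adds "Classification as a 300 mg responder and a 1000 mg responder are defined similarly".

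**The concern.** The two halves of item 4 call for different response variables, and the item is a formal test at two-sided 0.05. Someone programming from the definition would flag 300 mg responders among adults, test that variable, and publish the result under a 600 mg heading.

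That would also exchange the status of two adult results. The adult 300 mg response is otherwise exploratory: SAP 3.4 says "The first 3 key secondary endpoints will be repeated in the following 4 age groups", which include 18 to 55 years, and SAP 9.6.2 repeats the key secondary analyses in adults. Under the literal definition it would become confirmatory. The adult 600 mg response would still be produced, because 600 mg is the first Europe key secondary endpoint and is repeated in adults, but only as an exploratory result.

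**Working it through.** **1. Which cumulative amount belongs to which dose.** The Exit challenge doses in SAP Table 2.4, without the optional 1 mg dose, are 3, 10, 30, 100, 300, 600 and 1000 mg.

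- Through 300 mg: 3 + 10 + 30 + 100 + 300 = 443 mg
- Through 600 mg: 443 + 600 = 1043 mg
- Through 1000 mg: 1043 + 1000 = 2043 mg

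The 1043 mg in the heading of item 4 is reproduced and belongs to 600 mg. The heading is consistent within itself, and the 300 mg in the definition is a lower step of the challenge.

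**2. Heading against definition for the dose-response items in SAP 9.3.**

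| Item | Age group | Heading | Definition |
|---|---|---|---|
| North America 1 | 4-17 | 300 mg | 300 mg |
| North America 2 | 4-17 | 1000 mg | 1000 mg |
| North America 4 | 18-55 | 600 mg | **300 mg** |
| Europe 1 | 4-17 | 600 mg | 600 mg |
| Europe 2 | 4-17 | 300 mg | 300 mg |
| Europe 4 | 18-55 | 1000 mg | 1000 mg |

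Five of six agree. The corresponding adult item for Europe, "The proportion of subjects ages 18-55 who tolerate a single dose of 1000 mg of peanut protein", matches its heading. Item 3 in each list is symptom severity and has no dose threshold.

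**3. Other statements of the North America adult endpoint.** Protocol synopsis, protocol 3.7.1, protocol 9.2.2.1, SAP 1.1 and SAP 3.2.1: five statements, all at least 600 mg, none 300 mg.

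**4. How far the two variables can differ.** The documents give no adult response rates. ARC001 (protocol 1.2.2.1, ITT population) gives an indication:

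| Arm | 300 mg responders | 600 mg responders | Classified differently |
|---|---|---|---|
| AR101 | 23/29 (79%) | 18/29 (62%) | 23 − 18 = 5 |
| Placebo | 5/26 (19%) | 0/26 (0%) | 5 − 0 = 5 |

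The challenge ascends in a fixed sequence, so every 600 mg responder is also a 300 mg responder, and the differences count subjects whose class changes: (5 + 5)/(29 + 26) = 10/55 = 18%. The treatment difference hardly moves: 79% − 19% = 60% at 300 mg and 62% − 0% = 62% at 600 mg.

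**5. Size of the adult group.** Protocol 9.4 gives 554 − 495 = 59 adults enrolled and SAP 2.4 gives 555 − 499 = 56. At 3:1 that is about 14 or 15 on placebo (56/4 = 14; 59/4 = 14.75), so one reclassified placebo subject moves that arm's rate by about 7 percentage points (1/14 = 7.1%; 1/15 = 6.7%).

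**The case against.** The strongest reply is that this is a typing slip which the documents already resolve. The heading gives 600 mg together with its matching cumulative amount, SAP 3.2.1 states both the endpoint and its place in the order, and the protocol agrees. SAP 6.3 points to 9.3 for the testing method, so 9.3 is not the only source for the endpoint definition. SAP 15 requires independent confirmatory programming and senior review. The consequence is also limited: item 4 is the last key secondary endpoint, SAP 1.1 records the regulator's view that licensure will likely be possible only for ages 4 to 17, and SAP 9.5 makes no labeling claims from the other secondary endpoints.

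Most of this stands. The intended threshold can be recovered, SAP 3.2.1 is an equally valid source, and the ARC001 treatment difference is nearly the same at either threshold, so those data do not suggest that the test conclusion would change.

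It does not remove the error. SAP 9.3 is the section cited for the hierarchical tests. The step-by-step account of the North America sequence in protocol 9.2.2.1 stops at symptom severity, so SAP 9.3 is where the adult test is spelled out as a step. Independent programming is a weak safeguard here, because two programmers working from the same sentence could agree on the same wrong variable.

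**Conclusion.** The contradiction is real and lies in current SAP text. It is the only mismatch among the six dose-response items, and it falls on the response threshold of a listed key secondary test. It should be fixed.

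The effect is confined to that one adult test. Type I error is not inflated, because one test is still made at that step. The primary endpoint and the three pediatric key secondary endpoints ahead of it are untouched. What is at risk is that the wrong variable is tested and labeled as confirmatory.

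The 18% reclassification shows only that the two variables are not interchangeable. ARC001 covered ages 4 to 21, and protocol 6.1 says that Phase 2 enrolled a single adult, so neither the 18% nor the 60% and 62% differences should be read as adult estimates.

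**What to change.** Before database lock, reconcile the definition in SAP 9.3, North America item 4, with its own heading, SAP 3.2.1 and protocol 3.7.1, so that a single response threshold is stated and tested. Check that the table shells and the programming specification for this endpoint use the same responder class.

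SAP 6.5 already provides the route: a SAP amendment or a Note to File before lock. The cost is one figure in the text, with no extra data or analysis. After unblinding, the same correction could look like a choice of endpoint made with the results in view.
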